6. SELECTION OF PATIENTS AND DONORS

6.1. Screening Log

A screening log must be maintained and appropriately filed at site. Sites should record each patient screened for the trial and the reasons why they were not registered into the trial if this is the case. The log must be sent to UCL CTC when requested.

6.2. Patient Eligibility

There will be no exception to the eligibility requirements at the time of registration. Queries in relation to the eligibility criteria must be addressed prior to registration. Patients are eligible for the trial if all the inclusion criteria are met and none of the exclusion criteria applies.

Patients' eligibility must be confirmed by an investigator who is suitably qualified and who has been allocated this duty, as documented on the site staff delegation log, prior to registering the patient. Confirmation of eligibility must be documented in the patients' notes and on the registration CRF. Eligibility to receive trial treatment must also be confirmed prior to the patient receiving the CD62L⁻ Tem infusion and verified with UCL CTC.

Patients must give written informed consent before any trial specific screening investigations may be carried out. Refer to section 9.1 (Pre-Registration Assessments) for the list of assessments and procedures required to evaluate the suitability of patients prior to entry.

6.2.1. Patient Registration Inclusion criteria

- Severe aplastic anaemia or
- Primary immune deficiency or
- Haematological cancer which can be **ONE OF** the following (see Appendix 4 for complete response/remission (CR) and partial response/remission (PR) definitions):
 - $\circ~$ Non-Hodgkin's lymphoma (NHL) in CR or PR (and VGPR in applicable disease types)
 - Hodgkin's lymphoma (HL) in CR or PR
 - Chronic (Pro-)lymphocytic leukaemia (CLL or PLL) in CR, CRi or PR
 - Plasma cell myeloma (PCM) in CR, sCR, VGPR or PR
 - o Acute myeloid leukaemia (AML) in CR or CRi
 - Acute lymphoblastic leukaemia (ALL) in CR or CRi
 - Myelodysplastic syndrome (MDS) < 10 % blasts in bone marrow
 - Chronic myelomonocytic leukaemia (CMML) < 10% blasts in bone marrow
- Suitable for HLA-identical sibling transplant using a standard alemtuzumab-based conditioning regimen with calcineurin-inhibitor based immunoprophylaxis
- Aged \geq 16 years, <70 years
- Written informed consent

6.2.2. Patient Registration Exclusion criteria

- Women who are pregnant or breast-feeding
- Life expectancy of < 8 weeks
- Currently taking part in any other interventional clinical research study (involving any IMP, ATIMP or cellular therapy)
- Proposed use of any other method of GvHD prophylaxis other than alemtuzumab and calcineurin inhibitor
- Organ dysfunction:
 - LVEF <45%
 - glomerular filtration rate (corrected) <50ml/min
 - Bilirubin > 50 μmol/l
 - AST or ALT >2.5 x ULN (NB: If both are performed then both must be ≤2.5 x ULN)

6.2.3. Patient Trial Treatment Exclusion criteria

Following the stem cell transplant the following exclusion criteria must be checked within 2 days prior to the planned CD62L⁻ Tem infusion date. The patient's eligibility for trial treatment must be confirmed with UCL CTC prior to infusion taking place (see section 7.2) and continually assessed up to the point of Tem infusion.

- Prior or active acute pattern GvHD of any grade
- Relapse or progression
- Primary or secondary graft failure
- Has received other cellular therapies

6.3. Allogenic Donor Eligibility

There will be no exception to the eligibility requirements at the time of registration. Assessment of related donor eligibility is the responsibility of the site.

Donors must give written informed consent before any trial specific screening investigations may be carried out. Refer to section 9.1 (Pre-Registration Assessments) for the list of assessments and procedures required to evaluate the suitability of donors prior to entry.

6.3.1. Donor inclusion criteria

- Aged ≥ 16 years
- HLA-identical sibling
- Have met transplant centre criteria regarding suitability for cell therapy donation
- Negative for HIV 1 and 2, hepatitis B, hepatitis C, HTLV-1 and 2, syphilis serology (to be confirmed before both registration and at time of or up to 7 days following donation)
- Written informed consent

6.3.2. Donor exclusion criteria

• Pregnant/lactating women

6.4. Pregnancy and birth control

6.4.1. Definitions

Definition of women of childbearing potential (WOCBP) and fertile men

A woman of childbearing potential (WOCBP) is a sexually mature woman (i.e. any female who has experienced menstrual bleeding) who:

- Has not undergone a hysterectomy or bilateral oophorectomy/salpingectomy
- Is not postmenopausal (a post-menopausal woman is a female who has not had menses at any time in the preceding 12 consecutive months without an alternative medical cause)
- Has not had premature ovarian failure confirmed by a specialist gynaecologist

A man is considered fertile after puberty unless permanently sterile by bilateral orchidectomy.

6.4.2. Risk of exposure to trial treatment during pregnancy

CD62L⁻ Tem is a donor derived blood product with no manufacturing process and involves depletion of CD62L⁺ cells via immune-magnetic depletion. Although similar T-cell products have been used in donor lymphocyte infusions following allogeneic stem cell transplantation, there is currently no pre-existing safety data for the specific use of CD62L⁻ Tem in pregnant women. There is also a limited amount of data from the use of alemtuzumab in pregnant women and the exact drugs used during the alemtuzumab-based conditioning regimen will be dependent upon the treating site's standard of care. Side effects of allo-STC and CD62L⁻ Tem (e.g. GvHD) could necessitate other treatment that could also be a risk to a foetus.

Therefore, as the safety implications are unknown treatment has been assessed as having a high risk of teratogenicity/fetotoxicity. Female patients who are pregnant or who are breast feeding are excluded from entry into the trial.

6.4.3. Pregnancy testing

All female trial patients and female donors who are WOCBP must have a negative serum or negative highly sensitive urine pregnancy test (minimum sensitivity 25 IU/I or equivalent units of HCG) at prior to registration (see section 9.1). Pregnancy testing is repeated prior to Tem-infusion in patients only (see section 9.2).

6.4.4. Contraceptive advice

Requirement for female patients

All female trial patients who are WOCBP must consent to use one of the following methods of highly effective contraception from the start of treatment (Tem cells infusion) until 6 months post Tem infusion. Methods with low user dependency are preferable, particularly where introduced as a result of participation in the trial.

- combined (estrogen and progestogen containing) hormonal contraception associated with inhibition of ovulation:
 - oral

- intravaginal
- transdermal
- progestogen-only hormonal contraception associated with inhibition of ovulation:
 - oral (e.g. desogestrel)
 - injectable
 - implantable¹
- intrauterine device (IUD)¹
- intrauterine hormone-releasing system (IUS)¹
- bilateral tubal occlusion¹
- vasectomised partner^{1, 2}
- sexual abstinence³

•

1. Contraception methods that are considered to have low user dependency.

2. Vasectomised partner is a highly effective birth control method provided that partner is the sole sexual partner of the WOCBP trial patient and that the vasectomised partner has received medical assessment of the surgical success.

3. Sexual abstinence is considered a highly effective method only if defined as refraining from heterosexual intercourse during the entire period of risk associated with the study treatments. The reliability of sexual abstinence needs to be evaluated in relation to the duration of the clinical trial and the preferred and usual lifestyle of the subject.

Requirement for male patients with female partners who are pregnant or WOCBP

Due to the risk of genotoxicity and/or risk to the foetus from exposure to seminal fluid:

- Male patients (including male patients who have had vasectomies) must consent to use condoms with female partners who are WOCBP or partners who are pregnant, during treatment (inclusive of the conditioning regime) and until 6 months post Tem infusion.
- Male patients must also advise their female partners who are WOCBP regarding contraceptive requirements as listed for female patients who are WOCBP.

For female and male patients

The method(s) of contraception used must be stated in the patient medical notes. The medical notes of male participants should include a statement that the female partner has been informed about contraception advice.

6.4.5. Action to be taken in the event of a pregnancy

Female patients:

If a female patient becomes pregnant:

- prior to Tem infusion, the patient will be withdrawn from the trial and will not receive trial treatment.
- after Tem infusion, during the pregnancy at-risk period (until 6 months post infusion), the patient (or their female partner) will be followed up until 6 weeks after the end of the pregnancy if they consent to pregnancy monitoring.

Male patients:

If a female partner of a male patient becomes pregnant, or a pregnant female partner is exposed to trial treatment after Tem infusion and until 6 months post infusion, the male

patient can continue with the study whilst their female partner will be followed up if they have given consent to pregnancy monitoring.

Female donor:

If a female donor becomes pregnant prior to apheresis, the donor and respective patient will be withdrawn from the trial and the patient will not receive trial treatment.

Notification to UCL CTC

Refer to Pregnancy Report Processing (see Pharmacovigilance section 12.6)

6.4.6. Long term infertility

Studies to evaluate the effect of CD62L⁻ Tem on fertility have not been performed and the risk on male and female fertility is unknown. Patients who wish to have children in the future should be given advice regarding sperm or oocyte cryo-conservation prior to treatment in line with standard local policy.

6.4.7. Lactation

The effect of CD62L⁻ Tem in lactating females is currently unknown. In pre-clinical studies alemtuzumab was detected in the milk and offspring of lactating female mice. It is unknown whether alemtuzumab is excreted in human milk, and a risk to the suckling newborn/infant cannot be excluded. Therefore, females who are breast feeding are excluded from trial entry.

7. **REGISTRATION PROCEDURES**

There is a two-step registration process for ToTem:

- 1. Trial Registration Initial registration into the trial of the patient and donor prior to donor apheresis and patient transplant conditioning.
- Confirmation of eligibility for trial treatment after patient stem cell transplant and within 2 days prior to CD62L⁻ Tem infusion, patient eligibility for trial treatment should be reassessed (see section 6.2.3) and confirmed with UCL CTC.

7.1. Trial Registration

Registration will be undertaken centrally at UCL CTC and this must be performed **prior to donor apheresis and patient transplant conditioning**. Pre-registration evaluations for patients and donors should be carried out at sites as detailed in section 9.1 (Pre-Registration Assessments).

Following the pre-registration assessments, confirmation of eligibility, and the consent of the patient and donor at a site, the registration CRF must be fully completed and faxed to UCL CTC. This will be used to confirm patient and donor eligibility. If further information is required UCL CTC will contact the person submitting the registration form to discuss the patient and request updated forms to be faxed.

N.B. If the site is unable to fax, registration forms may be sent by email. If emailing forms, identifiable information on the form (e.g. date of birth) must be redacted before it is emailed to [contact]. The identifiable information must be provided to UCL CTC via telephone so that UCL CTC can transcribe this information onto the form. The un-redacted form must then be posted to UCL CTC, and a copy kept in the patient file at site.

Once eligibility has been confirmed a trial number (e.g. TOT-01) and cohort dose allocation will be assigned to the patient. The donor will also be assigned a trial number (e.g. TOT-01-D) which will link them to the trial patient.

UCL CTC will e-mail confirmation of the patient's inclusion in the trial, their trial number and cohort allocation to the PI, main contact and main research nurse (if different from main contact) and the cell processing laboratory (CCGTT). Details of this should be added to the registration form by the site.

Registration fax number: Registration email address: [name] [contact]

UCL CTC Office hours:

09:00 to 17:00 Monday to Friday, excluding Bank Holidays

Once registration has been completed the **patient and the donor** must be provided with the following:

- A copy of their signed consent form and patient/donor information sheet
- A patient contact card. Site contact details for 24 hour medical care must be added to this card. Patients should be advised to carry this with them at all times while participating in the trial.

After registration the ToTem GP letter **must be sent to the patient's GP** by the site to inform them they are participating in the trial.

7.2. Confirmation of eligibility for trial treatment

Eligibility for trial treatment must be confirmed with UCL CTC **prior to CD62L⁻ Tem infusion** (trial treatment) (see patient trial treatment exclusion criteria section 6.2.3). The Confirmation of Eligibility for trial treatment CRF must be faxed to UCL CTC **within 2 days prior to** the infusion taking place, allowing sufficient time for UCL CTC to process the CRF. If confirmation is required urgently (e.g. the CRF is faxed on the same day as the infusion) provide as much advance notice as possible and telephone the ToTem Trial Coordinator to inform them of this.

N.B. If the site is unable to fax, the Confirmation of eligibility for trial treatment CRF may be sent by email to [contact]. The identifiable information must be provided to UCL CTC via telephone so that UCL CTC can transcribe this information on to the form. The un-redacted form must then be posted to UCL CTC, and a copy kept in the patient file at site.

Once eligibility for trial treatment has been confirmed, UCL CTC will e-mail the PI, main contact and main research nurse (if different from main contact) confirming that the patient may proceed with trial treatment.

Registration fax number: Registration email address: [name] [contact]

UCL CTC Office hours:

09:00 to 17:00 Monday to Friday, excluding Bank Holidays

Evaluations for eligibility should be undertaken up until the time of the infusion and if the eligibility status of the patient changes (as per section 6.2.3 and section 15), treatment should be withheld and UCL CTC contacted immediately. Pre-treatment assessments should be performed as per section 9.3.

8. TRIAL TREATMENT

Investigational treatments

The investigational treatment is: Donor T cells depleted of CD62L⁺ cells (CD62L⁻ Tem).

8.1. Treatment Summary

Day number	Task
Day -14 to -7 (recommended) up to +24 permissible (with prior agreement from CCGTT lab)	Donor Tem Apheresis - Perform steady state lymphocyte collection
	Patient undergoes standard conditioning protocol
Day-1 to 0	Donor peripheral blood stem cell (PBSC) mobilization/ harvest or bone marrow harvest as per local policy
Day 0	Stem Cell Transplant
Day +24 to +32	Trial Treatment - Infuse CD62L ⁻ Tem
Day +100 to +180 (start taper at day +100 and aim to complete taper by day +180)	Tapering of calcineurin inhibitor in absence of GvHD

8.2. Treatment Details

8.2.1. Donor CD62L⁻ Tem Apheresis and PBSC/Bone marrow harvest

Following Trial Registration, the donor may undergo single steady state apheresis for the purpose of selecting CD62L⁻ Tem. The trial site must arrange the time and date of leukapheresis with the Centre for Cell, Gene and Tissue Therapeutics (CCGTT) as soon as possible after registration (see **Error! Reference source not found.**)

The preferred schedule is for donors to undergo apheresis between -14 to -7 days prior to day 0 of the stem cell transplant (the day when the stem cells are infused). The apheresis product will then be couriered to CCGTT and processed according to the patient's cohort. Following the steady state apheresis, donors will then undergo peripheral blood stem cell (PBSC) mobilization/harvest or bone marrow harvest according to local policies.

Because of the logistics involved in scheduling apheresis appointments and processing laboratory availability at each trial centre, it will also be permissible for donors to undergo a steady state apheresis after PBSC or bone marrow donation. Therefore, a maximum window for apheresis is allowed between -14 days prior to and up to +24 days following day 0 of the transplant with prior agreement from CCGTT.

8.2.2. Patient Conditioning and Stem Cell transplant

All patients will undergo a standard conditioning protocol employing immunoprophylaxis with alemtuzumab, in combination with a calcineurin inhibitor. This is standard treatment and the conditioning drugs and post-transplant immunosuppression are not considered IMPs for the purposes of the trial; nor is the transplant considered a trial-specific

procedure. Conditioning, transplant, post-transplant anti-microbial/anti-viral prophylaxis will be given in accordance with local policies.

8.2.3. Investigational Treatment - CD62L⁻ Tem infusion

Following the completion of the pre-treatment assessments (see section 9.3) and confirmation of eligibility for trial treatment (see section 7.2 and 6.2.3) patients may receive the CD62L⁻ Tem product.

The patient will have the donor CD62L⁻ Tem as a single infusion between day +24 and day +32 post-transplant. The site should request the CD62L⁻ product from CCGTT as described in **Error! Reference source not found.** of the Laboratory Manual. The product for re-infusion will be recovered from cryopreservation, thawed rapidly at 37°C and re-infused in less than 30 minutes after the thawing process is complete following local policy for infusion of T-cell by a suitably trained and accredited staff.

8.2.4. Post-Trial Treatment

In the absence of GvHD, tapering of calcineurin inhibitors will be from day +100 onwards with the aim that they are discontinued by day +180.

8.3. CD62L⁻ Tem Dose Levels

We will investigate 4 CD62L⁻ Tem dose levels $(1x10^{5}/kg, 3x10^{5}/kg, 1x10^{6}/kg)$ and $3x10^{6}/kg$. At the time of patient registration, UCL CTC will send an e-mail confirming the cohort the patient is in and the dose level they will receive.

The first two patients will receive dose level 3 (1x10⁶/kg), and then be followed for 72 days post Tem infusion to monitor for GvHD onset. Data from patients 1 and 2 will be used to update the prior DLT risks, and a formal Safety Review Committee (SRC) meeting will be held to recommend the dose to be given to patients 3 and 4. After following up patients 3 and 4 for 72 days post infusion to monitor for GvHD onset, another formal SRC meeting will be held to recommend the dose to be given to patients 5 and 6. From then, partial follow-up data from the 72 day DLT window will be used to estimate DLT risks on an ongoing basis, so that new patients who are recruited before previous patients have completed follow-up may be entered onto the trial and receive CD62L⁻ Tem. A minimum of two patients will be treated at open dose cohorts.

Dose Level	1	2	3	4
Dose:	1x10⁵/kg	3x10⁵/kg	1x10 ⁶ /kg	3x10 ⁶ /kg

We will use a two-parameter logistic model to describe the relationship between the dose of Tem and the probability of observing a DLT (acute GvHD grade II-IV). The MTD is the largest dose that can be given to trial patients that has an estimated probability of DLT no more than the target toxicity level of 20%. Skipping untested doses when escalating dose is prohibited.

The dose of cells infused will be determined in advance by the SRC. In all cases, the dose will be capped according to the total number of contaminating naïve T cells in the CD62L⁻ Tem product so that the dose of naïve T cells infused is < 0.05×10^{6} /kg recipient weight.

No dose reductions are permissible in this study. If the patient does not receive the full dose of the Tem product for any reason UCL CTC should be contacted immediately.

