17. STATISTICS

17.1. Sample Size Calculation

The trial will be conducted as a dose-escalation study and use the Time-to-event Continual Reassessment Method (TITE-CRM; (17)) to guide dose-escalation decisions. The study aim is to identify the Maximum Tolerated Dose (MTD) and thus the Recommended Phase II Dose (RP2D) of Tem when given following allogenic stem cell transplantation. Four dose levels will be available for investigation $(1\times10^5/kg, 3\times10^5/kg, 1\times10^6/kg, 3\times10^6/kg)$. The MTD is defined as the largest dose of Tem that has an estimated risk of causing DLT (acute-pattern GvHD grade II-IV) equal or closest to 20% (the target toxicity level). We assume the relationship between DLT risk and Tem dose can be estimated using a two-parameter logistic model. Before the trial, we assume that the prior risk of DLT at the highest dose $(3\times10^6/kg)$ is 20%. We then use the prior calibration method of (18) to provide working prior beliefs for dose-toxicity risks at the other doses; this gives median DLT risks (and 90% credible intervals) shown in Table 1.

Dose	1x10⁵/kg	3x10⁵/kg	1x10 ⁶ /kg	3x10 ⁶ /kg
Prior median	8%	11%	15%	20%
90% Credible Interval	(0, 56)	(1, 63)	(1, 71)	(2, 78)

Table 1: Prior median probabilities of DLT risk per dose (90% credible interval). Model parameters (intercept and log-slope) from bivariate Normal distribution with means (-1.39, -1.17) and independent variances (2.60, 0.22) respectively.

A minimum of two patients will be treated at open dose cohorts. The first two patients will receive dose level 3 ($1x10^{6}$ /kg), and be followed for 72 days post infusion to monitor for GvHD onset. Data from patients 1 and 2 will be used to update the prior DLT risks, and a formal SRC meeting will be held to recommend the dose to be given to patients 3 and 4. After following up patients 3 and 4 for 72 days post infusion to monitor for GvHD onset, another formal SRC meeting will be held to recommend the dose to be given to patients 5 and 6. From then (after patient 5 and 6 begin treatment), partial follow-up data from the 72 day DLT window will be used to estimate DLT risks on an ongoing basis, so that new patients who are recruited before previous patients have completed follow-up may be entered onto the trial and receive Tem. Computations for updating the model will be performed in R Software(19).

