The maximum sample size for this study is 18 patients. This was chosen based on projected recruitment timelines for eligible patients, and obtaining sensible operating characteristics from the design. The trial may be terminated early if either i) Tem dose is escalated to dose level 4 without any DLTs occurring and 6 patients are dosed at dose level 4 without experiencing DLT – dose level 4 will be declared as the MTD (total of 8 patients), or ii) the chance that the risk of DLT at the lowest dose being above the target toxicity level is at least 90% – the trial will be stopped for safety.

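### Sections 8.3 and 17.1 define the MTD by two different rules, so the same DLT data can give a different model-based MTD and hence RP2D

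*Protocol*

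**What the plan says.** Section 8.3 (CD62L⁻ Tem Dose Levels) makes the MTD the largest dose that "has an estimated probability of DLT no more than the target toxicity level of 20" per cent. Section 17.1 (Sample Size Calculation) makes it the largest dose with an "estimated risk of causing DLT (acute-pattern GvHD grade II-IV) equal or closest to 20% (the target toxicity level"). Neither section refers to the other's wording.

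Section 17.1 also fixes the model: "We assume the relationship between DLT risk and Tem dose can be estimated using a two-parameter logistic model". The note to Table 1 gives the prior: "Model parameters (intercept and log-slope) from bivariate Normal distribution with means (-1.39, -1.17) and independent variances (2.60, 0.22) respectively". Safety stopping rule (ii) applies when "the chance that the risk of DLT at the lowest dose being above the target toxicity level is at least 90" per cent.

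Under section 17.2.1 the final model estimates, together with SRC recommendations, determine the MTD and through it the RP2D.

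**The concern.** The MTD is the trial's primary answer and the RP2D follows from it. A ceiling rule never names a dose estimated above 20%. A closest-to-target rule will do so whenever the nearest estimate lies on the high side. The word largest in section 17.1 does not remove the difference, because it only settles ties.

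On some data the two sections therefore name different doses. Adjacent levels differ by a factor of 3 to 3.3, so the recommended cell dose would differ by about that much. A ceiling rule can also leave no qualifying dose, whereas a closest rule always returns one. That matters for how each definition fits with stopping rule (ii).

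**Working it through.** **Inputs.** Doses of 1×10⁵, 3×10⁵, 1×10⁶ and 3×10⁶/kg (sections 8.3 and 17.1). Prior for intercept *a* ~ N(−1.39, 2.60) and log-slope *b* ~ N(−1.17, 0.22), independent, second argument a variance (Table 1 note). Target 20%. Stop if P(risk at level 1 > 20%) ≥ 0.90. Maximum 18 patients.

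**Model.** logit p(d) = a + exp(b)·x(d), with x(d) = ln(dose/3×10⁶) = −3.401, −2.303, −1.099, 0. The protocol does not state this scaling. It is inferred because it puts the prior risk at the top dose at 20%.

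**Table 1 first.** At the prior means the slope is exp(−1.17) = 0.310. At level 4, p = 1/(1 + exp(1.39)) = 19.9%. At level 1, p = 1/(1 + exp(1.39 + 0.310×3.401)) = 8.0%. Levels 2 and 3 give 10.9% and 15.0%. The 90% intervals come out at 0.4-56, 0.7-63, 1.2-71 and 1.7-78%. The table (8/11/15/20%, with its intervals) is reproduced, so the inferred scaling is sound.

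**Posteriors.** The likelihood is the product over doses of p^y(1−p)^(n−y), with complete follow-up, evaluated on a numerical grid. Three readings of the estimated risk were tried: posterior median, posterior mean, and the plug-in value at the posterior means of *a* and *b*.

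| DLT data | Summary | Levels 1/2/3/4 (%) | 8.3 | 17.1 |
|---|---|---|---|---|
| 0/2 at level 3, 4/16 at level 4 | median | 8.0/11.1/15.8/21.6 | 3 | 4 |
| | mean | 9.2/12.3/16.9/22.7 | 3 | 4 |
| | plug-in | 8.4/11.5/16.0/21.3 | 3 | 4 |
| 4/18 at level 3 | median | 10.7/14.6/20.4/27.0 | 2 | 3 |
| | mean | 11.9/15.7/21.4/28.1 | 2 | 3 |
| | plug-in | 11.4/15.2/20.6/26.6 | 2 | 3 |
| 2/2 at level 3 | median | 42/51/60/68 | none | 1 |
| | mean | 44/51/58/65 | none | 1 |
| | plug-in | 45/53/61/69 | none | 1 |

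(A coarser grid gives 21.8% for the 21.6% entry; the doses named do not change.)

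Reading the medians:
- Row 1: level 4 is 21.6 − 20 = 1.6 points from target and level 3 is 20 − 15.8 = 4.2 points away. Section 17.1 takes level 4; section 8.3 excludes it.
- Row 2: level 3 is 0.4 points above target and level 2 is 5.4 below.
- Row 3: every estimate exceeds 20%, so no dose meets 8.3, and level 1 is nearest. P(level 1 risk > 20%) = 0.815, below 0.90, so rule (ii) does not stop the trial.

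**Data on which the rules agree.** 0/2 at level 3 gives medians 3.9/5.6/8.3/11.8%. 0/2 at level 3 plus 3/16 at level 4 gives 5.9/8.2/11.9/16.6%. Both rules name level 4 in each case, on all three summaries.

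**How often they differ.** 1,500 simulated trials per scenario: cohorts of two, complete follow-up, no skipping, both early stops, dosing steered by the 17.1 rule, and both definitions applied to the same final data. Ranges span the three summaries.

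| True risks (%) | Final MTD differs |
|---|---|
| 2/4/7/10 | 4-7% |
| 8/11/15/20 (Table 1) | 20-24% |
| 5/10/20/35 | 40-43% |
| 10/20/30/40 | 46-48% |

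The curves other than Table 1 are assumptions, and partial time-to-event follow-up was not modelled.

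**The case against.** The best defence is that the model does not fix the dose alone. The SRC sets each dose in advance (8.3), may de-escalate or suspend recruitment (14.4.5), and contributes to the final MTD (17.2.1). This stands, and it limits the consequence. It does not say which definition the committee is to be given.

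Four stronger readings are tempting, and the documents do not support them.

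- A reader might infer that the two rules always conflict. They do not, as the agreeing data sets show.
- A reader might infer that one MTD rule drives every cohort decision. Both sentences define the MTD. For cohort dosing, sections 8.3 and 17.1 say only that the data update the DLT risks and the SRC recommends a dose.
- A reader might infer that after 2/2 DLTs the trial must simply run on. Only the model-based stop fails to fire. A formal SRC meeting is required before patient 3. Section 17.3 allows stopping on the joint judgement of the IDMC and SRC, and section 16.3 on the recommendation of the TSC or IDMC.
- A reader might take smaller early data sets as proof. 1/2 at level 3 separates the rules on medians (level 1 against 2), but on plug-in values (17.6/22.9/29.9/37.3%) both name level 1. 0/2 at level 3 plus 2/4 at level 4 separates them on medians (level 2 against 3), but on means (14.5/18.9/25.1/32.3%) both name level 2.

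Two further cautions apply. The 4/18 case has a thin margin (20.4% against 20%). It would also need the SRC to hold every cohort at level 3, which neither rule suggests after 0/2 or 1/2 there. Finally, the posterior summary may properly be named in an SAP that is not shown, so its absence here is not a fault in itself.

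**Conclusion.** The point holds as a contradiction in the current text about the rule for the primary result. Identical DLT data can, but need not, give a different model-based MTD and hence RP2D, usually by one dose level. The three tabulated cases do not depend on whether the median, mean or plug-in value is used. They rest on the stated prior, the inferred dose scaling and complete follow-up.

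The frequency depends on the unknown true risks. The range from 4-7% to 46-48% of simulated trials is indicative only and is not a property of the protocol. Where no dose meets the 8.3 definition and rule (ii) is not met, the matter passes to SRC, IDMC and TSC judgement with no model-based answer under 8.3.

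**What to change.** Reconcile sections 8.3 and 17.1 to one identical MTD definition, namely the one under which the operating characteristics for the maximum of 18 patients were obtained. Name the posterior summary it applies to, in the protocol or by reference to the SAP. Make the definition consistent with stopping rule (ii), so that data on which no dose meets it are covered. Which definition to keep, and what follows in that situation, is for the sponsor and the SRC to decide.

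The cost is one wording amendment. The operating characteristics need re-running in the existing R code only if the retained rule is not the one that was simulated, which the protocol does not show.
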